7.4.3 Other Efficacy Analyses

If there is a high study withdrawal rate before the second biopsy for reasons other than the final termination of the study then patterns associated with subject withdrawal will be analyzed with respect to the primary bone biopsy endpoints. If the patterns associated with early withdrawal suggest a possible source of bias, then a sensitivity analysis on the primary efficacy analyses using multiple imputation (Proc MI in SAS) will be employed.

The tertiary outcomes include changes in blood chemistries, FGF23, renal mineral handling, and PTH sensitivity will be analyzed using repeated measures if the outcome is continuous or using contingency tables for categorical outcomes. Results will be summarized in tables. Figures will be provided upon request.

8. SAFETY EVALUATION

Safety evaluation will include all tables and listings previously provided for the DSMB.

Additional safety tables and listing will be provided if requested by the study PI.

9. CHANGES TO THE ANALYSES PLANNED IN THE PROTOCOL

The study was discontinued early, due to pharmacy issues. Upon termination of new enrollment in June of 2015, subjects began to be slowly weaned off of hPTH. Of the 32 planned, newly enrolled subjects, only 19 were actually enrolled and treated and of these, 8 subjects provided their on-treatment biopsy. This early termination provides less power to detect significant differences in endpoints. We will evaluate the possibility of combining the 2- and 4- year biopsy groups to address this issue (see section 7.4.1 for details).

The primary bone biopsy endpoints have changed. The original primary endpoints included: 1) mineralized perimeter; 2) bone formation rate; 3) cortical width; 4) cortical area; 5) osteoid width; 6) osteoid perimeter; and 7) mineral apposition rate. These primary bone biopsy endpoints have been replaced with the eight primary endpoints listed in section 7.2.1. In the analysis of the pilot study of the first 5 patients as well as other relevant pilot studies, we learned that these are the more informative indices.

The primary and secondary analyses will be performed using repeated measures mixed models rather than the paired t-tests, ANOVA, and ANCOVA analyses as stated in the protocol.

Although the protocol specifies imputation analyses for all secondary endpoints collected every 6 months over the 5-year study period, for purposes of efficiency the sensitivity analyses using multiple imputation (Proc MI in SAS) of missing values will be initially limited to the primary efficacy bone biopsy endpoints. After reviewing patterns of missing-ness in the secondary endpoints, additional sensitivity analyses involving multiple imputations may be performed at the request of the PI.

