756 and 4 years of HPTH therapy. Those changes will be determined from antibiotic-labeled biopsies taken
757 before and during HPTH therapy. The static and dynamic bone histomorphometry variables that will be
758 assessed as primary outcomes are listed in the following:

- 759 1. Mineralized perimeter

- 760 2. Bone formation rate
- 761 3. Cortical width
- 762 4. Cortical area
- 763 5. Osteoid width
- 764 6. Osteoid perimeter
- 765 7. Mineral apposition rate

766 9.2 Secondary Outcome Measures

767 The secondary outcome measures are listed below:

- 768 1. Changes in bone mineralization density distribution will be assessed in bone biopsies by back-
769 scattered electron imaging at 1, 2 and 4 years of HPTH therapy. The specific outcomes that will
770 be measured include:
 - 771 a. spectral calcium-mean
 - 772 b. calcium-peak
 - 773 c. calcium-width
- 774 2. Non-biopsy outcomes are being measured every 6 months (annually for some outcomes) over
775 the 5 years of HPTH therapy. Changes from baseline in the following outcomes will be
776 assessed:
 - 777 a. Biochemical markers of bone metabolism: osteocalcin, bone-specific alkaline phosphatase,
778 collagen cross-linked N-telopeptide.
 - 779 b. Serum and urine calcium; 1,25-OH₂-Vitamin D
 - 780 c. Bone density assessed by DXA and quantitative CT
 - 781 d. Nephrocalcinosis by ultrasound and CT
 - 782 e. Fatigue Symptom Inventory
 - 783 f. 6-Minute Walk Test
 - 784 g. SF-36 Health Survey

785 Where appropriate, biochemical and biopsy data will be compared to age, sex, and ethnicity-matched
786 controls.

787 **9.3 Tertiary Outcome Measures**

788 The tertiary outcomes are early changes in blood chemistries and FGF23, renal mineral handling, and
789 PTH sensitivity with the initiation of HPTH. Tertiary outcome measures include:

- 790 a. Serum albumin, calcium, phosphorus, magnesium, sodium, potassium, chloride, Total CO₂,
791 creatinine, glucose, urea nitrogen, and FGF23
- 792 b. Urine cAMP, creatinine, phosphorus, calcium, and pH

793

794 **10 STATISTICAL ANALYSIS**

795 **10.1 Analysis of Data/Study Outcomes**

796 The overall analysis objective is to utilize exploratory and hypothesis testing methods to characterize the
797 response profile over time to HPTH therapy in the primary and secondary endpoints. The bone biopsy
798 measures are assessed at baseline and at 1, 2, and 4 years in 3 separate arms, while most other endpoints

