7.2 Efficacy Analysis

7.2.1 Primary Study Endpoints

The primary endpoints are changes in static and dynamic bone histomorphometry after 1 year, 2 years, and 4 years of hPTH therapy. These changes will be determined from antibiotic-labeled biopsies taken before and during hPTH therapy. The original protocol called for analyzing 7 bone markers of static and dynamic bone histomorphometry but the SAP has changed these to 8 bone markers of bone structure and bone remodeling. Analyses will be done on z-scores, when normative data are available. These are listed as follows:

7.2.1.1 *Bone Structure*

1. Cn.BV/TV: cancellous bone volume
2. Ct.Po.N: total number of cortical porosity per mm²

7.2.1.2 *Cancellous Bone Remodeling*

1. Cn.BFR/BS: Cancellous bone formation rate
2. Cn.MS/BS: Cancellous mineralizing surface (bone surface based)

7.2.1.3 *Endocortical Bone Remodeling*

1. Ec.BFR/BS: Endocortical bone formation rate
2. Ec.MS/BS: Endocortical mineralizing surface (bone surface based)

7.2.1.4 *Intracortical Bone Remodeling*

1. Ic.BFR/BS: Intracortical bone formation rate
2. Ic.MS/BS: Intracortical mineralizing surface (bone surface based)

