7.2.2 Secondary Study Endpoints

7.2.2.1 *Static and dynamic bone histomorphometry (After 1, 2, and 4 years of hPTH) in secondary bone biomarkers*

Analyses relating to bone endpoints listed below will be done on z-scores, when normative data are available.

1. Bone Structure
 - a. Tb.Th: Trabecular Thickness
 - b. Tb.N: Trabecular Number
 - c. Tb.Sp: Trabecular Separation
 - d. Ct.Th: Average Thickness of Inner and Outer Cortices
 - e. Ct.Ar: Total Area of Inner and Outer Cortices
 - f. Ct.Po.Ar: Total Area of Cortical Porosity
2. Cancellous Bone Remodeling
 - a. Cn.O.Th: Osteoid Thickness
 - b. MAR: Bone Mineral Apposition Rate
 - c. OS/BS: Osteoid Surface / Bone Surface
 - d. ES/BS: Eroded Surface / Bone Surface
 - e. AjAR: Adjusted Apposition Rate
3. Endocortical bone remodeling
 - a. Ec.O.Th: Osteoid Thickness
 - b. Ec.MAR: Bone Mineral Apposition Rate
 - c. Ec.OS/BS: Osteoid Surface/Bone Surface
 - d. ES/BS: Eroded Surface / Bone Surface

- e. AjAR: Adjusted Apposition Rate
- 4. Intracortical bone remodeling
 - a. O.Th: Osteoid Thickness
 - b. MAR: Bone Mineral Apposition Rate
 - c. OS/BS: Osteoid Surface / Bone Surface
 - d. ES/BS: Eroded Surface / Bone Surface
 - e. AjAR: Adjusted Apposition Rate

7.2.2.2 *Changes in bone mineralization density (BMD) distribution will be assessed in bone biopsies by back-scattered electron imaging at 1, 2 and 4 years of hPTH therapy. The specific outcomes that will be measured include:*

Analyses will be done on z-scores, when normative data are available.

- 1. Spectral calcium-mean
- 2. Calcium-peak
- 3. Calcium-width
- 4. Calcium low
- 5. Calcium high

7.2.2.3 *Non-biopsy outcomes are being measured every 6 months (annually for some outcomes) over the 5 years of hPTH therapy. Changes from baseline in the following outcomes will be assessed:*

- 1. Biochemical markers of bone metabolism: osteocalcin, bone-specific alkaline phosphatase, collagen cross-linked N-telopeptide.
- 2. Serum and urine calcium; 1,25-OH₂-Vitamin D
- 3. Bone mineralization density assessed by DXA and quantitative CT including both raw and z-scores (based upon sex and age). These will include measures at the following anatomical sites
 - a. AP Spine
 - b. Lateral Spine

- c. Femoral Neck
- d. Total Hip
- e. 1/3 Radius
- f. Whole Body

The quantitative CT is limited to only the spine.

- 4. Nephrocalcinosis and Nephrolithiasis by ultrasound and CT
- 5. Fatigue Symptom Inventory
- 6. 6-Minute Walk Test
- 7. SF-36 Health Survey

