7.4.1 Primary Efficacy Analyses

Separate primary analyses will be performed for each of the eight primary bone structure and bone remodeling biopsy endpoints listed in section 7.2.1. Since the study was terminated early and is thus under-powered, no corrections for multiplicity will be made in the analyses of the 8 primary efficacy endpoints. For each of these primary bone biopsy endpoints, the primary analysis will test for differences with respect to the time of the biopsy (baseline, 1, 2, and 4 year). These endpoints will be analyzed using repeated measures mixed models with the bone biopsy endpoint as the dependent variable, the baseline value of the bone biopsy endpoint and study cohort as covariates, biopsy time (baseline, 1 year, 2 year, and 4 year) as the repeated measure, and subject as the random variable. The repeated measures will include a time-dependent covariate to adjust the baseline biopsy of Cohort 2 for the time delay between the baseline biopsy and the start of hPTH treatment. This covariate will adjust Cohort 2 for any possible further progression of disease occurring between the baseline biopsy measures and the start of hPTH therapy. An indicator variable in the statistical model will set the effects of this time-dependent covariate to zero for Cohort 3 and for the post-baseline biopsies of Cohort 2.

Pairwise contrasts between the bone biopsy times will be performed within the repeated measures analyses to compare the effects of the biopsy times on the bone biopsy endpoints. Because the sample size for 2-year and 4-year biopsies are reduced in size due to withdrawal and the early termination of the study, the 2-, and 4-year biopsies may be combined into one group provided their effects are qualitatively similar (i.e. the estimates of their effects are in the same direction). If the 2- and 4-year biopsies are qualitatively different then the 4-year biopsies may be dropped from the analysis due to its small sample size. The post hoc pairwise comparisons among the

biopsy time-points will be corrected for multiple comparisons using Fisher's protected LSD with Bonferroni corrections when the overall effect of biopsy year is not statistically significant.

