10. LIST OF PLANNED TABLES

Subject listings associated with the tables below will be provided. Experimental time refers to the baseline, last hPTH treatment, and post-hPTH follow-up visits. Additional tables (eg, those based on the results of sensitivity analysis) will be provided. Other displays, as requested by the PI may be provided as well.

Table Type	Table
Disposition	Summary of Subject Disposition
Demographics	Summary of Study Enrollment by Demographic Characteristics
hPTH Therapy	Summary of the Duration of hPTH Therapy
Primary Efficacy	Summary Statistics of Primary Bone Biopsy Endpoints by Biopsy Year. (Separate tables for Cohorts 2, 3, and Cohort 2 combined with Cohort 3)
	Repeated Measures Analysis of Primary Efficacy Analysis (Separate tables for Cohorts 2, 3, and Cohort 2 combined with Cohort 3)
Secondary Efficacy	Summary of Bone Mineralization Density Assessed by Back-Scattered Electron Imaging by Years of hPTH therapy
	Summary of Biochemical Markers of Bone Metabolism by Experimental Time Including the Statistical Significance of Changes.
	Summary of Blood and Urine Chemistries by Experimental Time Including the Statistical Significance of Changes.
	Summary of Bone Mineralization Density Assessed by DXA and Quantitative CT by Experimental Time Including the Statistical Significance of Changes.
	Summary of Nephrocalcinosis and Nephrolithiasis by Time on Study Drug
	Summary of Fatigue Symptom Inventory and 6-Minute Walk Test by Experimental Time Including the Statistical Significance of Changes.
	Summary of SF-36 Health Survey by Experimental Time Including the Statistical Significance of Changes.
Adverse Events (as provided to DSMB)	Summary of Adverse Events Occurring While on hPTH 1-34 or After Withdrawal from hPTH 1-34
	Summary of Adverse Events Occurring on or after hPTH 1-34
	Summary of Adverse Events Occurring While on Conventional Care
	Summary of Adverse Events for Subjects on Conventional Care
	Summary of Adverse Events Occurring While on hPTH 1-34 or After Withdrawal from hPTH 1-34: Current PI
	Summary of Adverse Events Occurring While on hPTH 1-34 or After Withdrawal from hPTH 1-34: Prior to Current PI
	Summary of Adverse Events Occurring While on Conventional Care: Current PI
	Summary of Adverse Events Occurring While on Conventional Care: Prior to Current PI

	Summary of Adverse Events Occurring While on hPTH 1-34 or After Withdrawal from hPTH 1-34; Related (Unlikely, Possible, Probable, or Definite) to hPTH 1-34

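### Five of the protocol's seven primary bone endpoints became secondary in a SAP written after the trial stopped, with no model set out and no table named for them

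*SAP*

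**What the plan says.** Protocol 9.1 introduces its list with "The static and dynamic bone histomorphometry variables that will be" and, on the next line, "assessed as primary outcomes are listed in the following". Seven measures follow: mineralized perimeter, bone formation rate, cortical width, cortical area, osteoid width, osteoid perimeter and mineral apposition rate. None is tied to a bone compartment. The Précis gives the same seven. This is version 17.0, dated 9 September 2015.

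SAP Section 9 names the seven and then states: "These primary bone biopsy endpoints have been replaced with the eight primary endpoints listed in section 7.2.1". Its reason is that the first 5 patients and other, unnamed, pilot studies showed the new indices to be more informative. SAP 7.2.1 also declares the change. Section 9 dates the stop: "Upon termination of new enrollment in June of 2015, subjects began to be slowly weaned off of hPTH". It reports 19 new subjects enrolled and treated, of whom 8 gave an on-treatment biopsy. SAP 7.4.1 begins its multiplicity decision with "Since the study was terminated early and is thus under-powered" and makes no correction across the eight.

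The measures that lost primary status appear in SAP 7.2.2.1, titled "Static and dynamic bone histomorphometry (After 1, 2, and 4 years of hPTH) in secondary bone biomarkers". For histomorphometry, Section 10 names "Summary Statistics of Primary Bone Biopsy Endpoints by Biopsy Year" and a companion table for the repeated measures primary analysis.

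**The concern.** Two features combine. The choice of primary endpoints was revised in a single-group study when on-treatment biopsies already existed. The measures that lost primary status then went to the one group of secondary endpoints for which the SAP neither sets out a model nor names a table.

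With few paired biopsies and no correction across the eight primaries, the choice of what to call primary shapes the main publication. A reader who cannot see the protocol's own primaries, under the same model, cannot judge whether they agree with the revised set. The analyst is also left free to choose how those measures are modelled and whether they are shown.

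**Working it through.** **1. Timing.** The SAP text refers to the termination as past (7.4.1, Section 9), so it post-dates the June 2015 enrolment stop. The protocol version that still lists seven primaries is dated September 2015, also after the stop. The SAP does not say whether any on-treatment biopsy of Cohort 2 or 3 had been read when the list changed.

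**2. Where each protocol primary went.** The match is by concept (perimeter to surface, width to thickness). The SAP does not state it term by term.

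| Protocol 9.1 | SAP variable | SAP status |
|---|---|---|
| Mineralized perimeter | MS/BS: Cn, Ec, Ic | Primary |
| Bone formation rate | BFR/BS: Cn, Ec, Ic | Primary |
| Cortical width | Ct.Th | Secondary, 7.2.2.1 item 1d |
| Cortical area | Ct.Ar | Secondary, item 1e |
| Osteoid width | O.Th, three envelopes | Secondary, items 2a, 3a, 4a |
| Osteoid perimeter | OS/BS, three envelopes | Secondary, items 2c, 3c, 4c |
| Mineral apposition rate | MAR, three envelopes | Secondary, items 2b, 3b, 4b |

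- Of seven: 2 kept, 5 demoted, 0 removed; 5/7 = 71% demoted.
- New primary set: 2 measures × 3 envelopes + Cn.BV/TV + Ct.Po.N = 8. Only the last two are new constructs.
- Demoted concepts as SAP variables: 2 + 3 × 3 = 11.

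**3. Which endpoint groups have a model and a table.**

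| SAP endpoint group | Model set out in | Named table in Section 10 |
|---|---|---|
| 7.2.1, eight primaries | 7.4.1, extended in 7.4.2.1 and 7.4.2.2 | Yes |
| 7.2.2.1, secondary histomorphometry | None | None |
| 7.2.2.2, back-scatter imaging | 7.4.2.3 | Yes |
| 7.2.2.3, non-biopsy outcomes | 7.4.2.4 to 7.4.2.6 | Yes |
| 7.3, tertiary | 7.4.3 | Not named, but 7.4.3 promises tables |

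Among the secondary groups, only the one holding the five former primaries lacks both.

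**4. What the general statements leave open.** SAP 7.2.2.1 sets z-scores where norms exist. SAP 7.4 assigns the Bone Biopsy Population. Section 9 says that primary and secondary analyses use repeated measures mixed models. None of these settles the baseline and cohort covariates, the Cohort 2 term for the delay between baseline biopsy and treatment, the rule for pooling years 2 and 4, or the correction of contrasts. The two biopsy models that the SAP does set out differ on this. SAP 7.4.1 has the delay term and pools if the estimates share a direction. SAP 7.4.2.3 has no delay term and pools if effect sizes and variances look similar. Nothing says which one governs 7.2.2.1.

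**5. The stated reason.** The results from 5 subjects with baseline and 1-year biopsies are already in the protocol: they appear in the Introduction and are the basis of Protocol 10.2. Protocol 7.10.4 also already reports increased cortical porosity. The protocol held this information and kept the seven. If Section 9's first 5 patients are these subjects, that evidence does not explain why the list changed only in the SAP.

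**6. Sizing.** Protocol 10.2 rests on mineralizing perimeter and bone formation rate. For a paired t-test with n = 8, change 10, SD 7 and two-sided alpha 0.05, the noncentrality is (10/7) × √8 = 4.04 on 7 df. Power is 93.1%, against 93% stated. Both sizing endpoints remain primary, so the swap does not touch this calculation.

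**7. Multiplicity.** The protocol also tests each of its seven at 0.05. Under independence, an assumption made only for scale, the chance of at least one false positive is 1 − 0.95⁷ = 0.30 for seven and 1 − 0.95⁸ = 0.34 for eight. The swap barely changes this. The issue is which endpoints are chosen and shown.

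**The case against.** The change is declared twice, the replaced endpoints are listed, and a reason is given. If the first 5 patients are those in Protocol 10.2, they received HPTH under the former protocol. They would then fall in Cohort 1, which SAP Section 4 keeps out of the efficacy analyses, so that part of the stated basis would lie outside the data being tested. The SAP calls itself abbreviated. SAP 7.4 says that endpoints used in analyses will be tabulated, Section 4 repeats all efficacy analyses in Cohort 3, and Section 10 promises additional tables. A protocol version issued after the stop may simply have left the endpoint section untouched.

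Most of this stands, and it rules out three stronger readings that a reader might infer.

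- *The five measures have no analysis and will go unreported.* They are listed secondary endpoints with a scale, a population and a class of model. A missing named table is not a decision to withhold results.
- *Six of the eight new primaries have no counterpart in the protocol.* Protocol 9.1 names no compartment, and the word cancellous enters only in the power section. Endocortical and intracortical MS and BFR can be read as versions of protocol primaries.
- *The endpoints were chosen on their results.* The documents do not say that any Cohort 2 or 3 biopsy result had been seen.

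The general statements do not close the gap. The tabulation rule applies only to endpoints that are analysed. Section 10 gives sensitivity analyses as its example of additional tables and leaves other displays to the PI's request.

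**Conclusion.** The point holds as a gap in specification and reporting. Five of seven protocol primaries were demoted in a SAP written after termination, when on-treatment biopsies existed. They correspond to 11 SAP variables with no model set out in 7.4 and no named table in Section 10. Selective reporting is possible; the documents do not show that it is intended. The evidence cited for the change does not account for its timing.

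The conclusion assumes the concept-level match in the first table above, and that the 5 patients cited in SAP Section 9 are those in Protocol 10.2. If they are different patients, the timing argument weakens but the gap in model and tables remains. The two endpoints that sized the trial are unaffected. The change should be made, but the point does not invalidate the revised primary analysis.

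**What to change.** 1. State in SAP 7.4 that the 7.4.1 model applies to the SAP variables for all seven protocol primaries, with the same covariates, Cohort 2 baseline-delay term, pooling rule and contrasts. Six of those variables are already covered. The 11 to add are Ct.Th, Ct.Ar, and O.Th, OS/BS and MAR in each of three envelopes.
2. Add tables to Section 10 labelled *protocol-specified primary endpoints* beside those for the eight, and label the eight *revised after termination*.
3. State in Section 9 whether any on-treatment biopsy results from Cohort 2 or 3 had been seen when the list changed.

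Cost: SAP wording plus 11 × 2 = 22 more fits, counting the Cohort 3 repeat that Section 4 requires. This becomes 11 × 3 = 33 if Cohort 2 is also fitted alone, as the Section 10 table list implies. Copying the Section 10 layout (two table types for Cohort 2, Cohort 3 and combined) adds 2 × 3 = 6 tables. The drawback is more unadjusted p-values on a small sample, which the tables should say plainly.

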10. LIST OF PLANNED TABLES

Subject listings associated with the tables below will be provided. Experimental time refers to the baseline, last hPTH treatment, and post-hPTH follow-up visits. Additional tables (eg, those based on the results of sensitivity analysis) will be provided. Other displays, as requested by the PI may be provided as well.

Table Type	Table
Disposition	Summary of Subject Disposition
Demographics	Summary of Study Enrollment by Demographic Characteristics
hPTH Therapy	Summary of the Duration of hPTH Therapy
Primary Efficacy	Summary Statistics of Primary Bone Biopsy Endpoints by Biopsy Year. (Separate tables for Cohorts 2, 3, and Cohort 2 combined with Cohort 3)
	Repeated Measures Analysis of Primary Efficacy Analysis (Separate tables for Cohorts 2, 3, and Cohort 2 combined with Cohort 3)
Secondary Efficacy	Summary of Bone Mineralization Density Assessed by Back-Scattered Electron Imaging by Years of hPTH therapy
	Summary of Biochemical Markers of Bone Metabolism by Experimental Time Including the Statistical Significance of Changes.
	Summary of Blood and Urine Chemistries by Experimental Time Including the Statistical Significance of Changes.
	Summary of Bone Mineralization Density Assessed by DXA and Quantitative CT by Experimental Time Including the Statistical Significance of Changes.
	Summary of Nephrocalcinosis and Nephrolithiasis by Time on Study Drug
	Summary of Fatigue Symptom Inventory and 6-Minute Walk Test by Experimental Time Including the Statistical Significance of Changes.
	Summary of SF-36 Health Survey by Experimental Time Including the Statistical Significance of Changes.
Adverse Events (as provided to DSMB)	Summary of Adverse Events Occurring While on hPTH 1-34 or After Withdrawal from hPTH 1-34
	Summary of Adverse Events Occurring on or after hPTH 1-34
	Summary of Adverse Events Occurring While on Conventional Care
	Summary of Adverse Events for Subjects on Conventional Care
	Summary of Adverse Events Occurring While on hPTH 1-34 or After Withdrawal from hPTH 1-34: Current PI
	Summary of Adverse Events Occurring While on hPTH 1-34 or After Withdrawal from hPTH 1-34: Prior to Current PI
	Summary of Adverse Events Occurring While on Conventional Care: Current PI
	Summary of Adverse Events Occurring While on Conventional Care: Prior to Current PI

	Summary of Adverse Events Occurring While on hPTH 1-34 or After Withdrawal from hPTH 1-34; Related (Unlikely, Possible, Probable, or Definite) to hPTH 1-34
	Summary of Adverse Events Occurring While on hPTH 1-34 or After Withdrawal from hPTH 1-34
	Summary of Adverse Events Occurring on or after hPTH 1-34
	Summary of Adverse Events Occurring While on Conventional Care
	Summary of Adverse Events for Subjects on Conventional Care
	Summary of Adverse Events Occurring While on hPTH 1-34 or After Withdrawal from hPTH 1-34: Current PI
	Summary of Adverse Events Occurring While on hPTH 1-34 or After Withdrawal from hPTH 1-34: Prior to Current PI
	Summary of Adverse Events Occurring While on Conventional Care: Current PI
	Summary of Adverse Events Occurring While on Conventional Care: Prior to Current PI
	Summary of Adverse Events Occurring While on Conventional Care: Events During the Reporting Period
	Summary of Adverse Events Occurring While on hPTH 1-34 or After Withdrawal from hPTH 1-34: Current PI
	Summary of Adverse Events Occurring While on hPTH 1-34 or After Withdrawal from hPTH 1-34: Prior to Current PI
	Summary of Adverse Events Occurring While on Conventional Care: Current PI
	Summary of Adverse Events Occurring While on Conventional Care: Prior to Current PI
	Summary of Exposure to hPTH at Time of First On-Treatment Event within a Subject and SOC/Preferred Term Includes Only Events Occurring for ≥ 3 Subjects Within a Category
Protocol Deviations (as provided to DSMB)	Summary of Protocol Deviations
